10.3.5.1.2 Unsolicited Adverse Event Intensity Grading Scale

For measurable unsolicited AEs that are part of the list of solicited reactions, the corresponding scale for solicited reactions will be used (see Section 10.3.5.1.1).

All other unsolicited AEs will be classified according to the following intensity scale:

- Grade 1
 - CRF: A type of AE that is usually transient and may require only minimal treatment or therapeutic intervention. The event does not generally interfere with usual activities of daily living
 - DC: No interference with usual activities
- Grade 2
 - CRF: A type of AE that is usually alleviated with additional therapeutic intervention. The event interferes with usual activities of daily living, causing discomfort but poses no significant or permanent risk of harm to the research participant
 - DC: Some interference with usual activities
- Grade 3
 - CRF: A type of AE that interrupts usual activities of daily living, or significantly affects clinical status, or may require intensive therapeutic intervention
 - DC: Significant; prevents usual activities

10.4 Appendix: Collection of Pregnancy Information

DEFINITIONS:

Women of Childbearing Potential

A woman is considered fertile following menarche and until becoming postmenopausal unless permanently sterile (see below).

If fertility is unclear (eg, amenorrhea in adolescents or athletes) and a menstrual cycle cannot be confirmed before first dose of study intervention, additional evaluation should be considered.

Women in the Following Categories are not Considered Women of Childbearing Potential

- 1) Premenarchal
- 2) Premenopausal female with one of the following:
 - Documented hysterectomy
 - Documented bilateral salpingectomy
 - Documented bilateral oophorectomy

For individuals with permanent infertility due to an alternate medical cause other than the above, (eg, mullerian agenesis, androgen insensitivity), Investigator discretion should be applied to determining study entry.

Note: Documentation can come from the site personnel's: review of the participant's medical records, medical examination, or medical history interview.

- 3) Postmenopausal female
 - A postmenopausal state is defined as no menses for 12 months without an alternative medical cause.
 - A high follicle stimulating hormone (FSH) level in the postmenopausal range may be used to confirm a postmenopausal state in women not using hormonal contraception or hormonal replacement therapy (HRT). However, in the absence of 12 months of amenorrhea, confirmation with more than 1 FSH measurement is required.
 - Females on HRT and whose menopausal status is in doubt will be required to use one of the non-estrogen hormonal highly effective contraception methods if they wish to continue their HRT during the study. Otherwise, they must discontinue HRT to allow confirmation of postmenopausal status before study enrollment.

COLLECTION OF PREGNANCY INFORMATION

Female Participants who Become Pregnant

- The Investigator will collect pregnancy information on any female participant who becomes pregnant while participating in this study. The initial information together with the contraceptive method if any will be recorded on the appropriate form and submitted to the Sponsor within 1 month of learning of a participant's pregnancy. If the Electronic DC (EDC) system is not available, the Investigator must fill out a paper Pregnancy Reporting Form (provided by the Sponsor at the start of the study) and inform the Sponsor within 1 month of identifying a pregnancy case.
- The participant will be followed to determine the outcome of the pregnancy. Study staff must maintain contact with the participant to obtain information about the outcome (ie, details about the delivery and the newborn, or about pregnancy termination) and must update the Pregnancy Reporting forms even after the end of the study. This information should be provided to the Sponsor within 1 month of delivery by Investigator.
- For live births, an additional follow-up will be conducted 6 months after the delivery date to determine if any congenital anomalies in the infant not detected at birth have been diagnosed. An Infant Data Collection Form will be used for this purpose. Up to 3 follow-up attempts will be conducted with the child's physician or hospital (in cases of adverse outcome involving hospitalization). Any termination of pregnancy will be reported, regardless of fetal status (presence or absence of anomalies) or indication for the procedure.
- While pregnancy itself is not considered to be an AE or SAE, any pregnancy complication or elective termination of a pregnancy for medical reasons will be reported as an AE or SAE.

- A spontaneous abortion (occurring at < 22 weeks gestational age) or still birth (occurring at > 22 weeks gestational age) is always considered to be an SAE and will be reported as such.
- Any post-study pregnancy related SAE considered reasonably related to the study intervention by the Investigator will be reported to the Sponsor as described in Section 8.3.4. While the Investigator is not obligated to actively seek this information in former study participants, he or she may learn of an SAE through spontaneous reporting.

CONTRACEPTION GUIDANCE

•	CONTRACEPTIVES ^a ALLOWED DURING THE STUDY INCLUDE:
• co	Highly Effective Methods^b That Have Low User Dependency Failure rate of <1% per year when used nsistently and correctly.
٠	Implantable progestogen-only hormone contraception associated with inhibition of ovulation ^b
٠	Intrauterine device (IUD)
٠	Intrauterine hormone-releasing system (IUS) ^b
٠	Bilateral tubal occlusion
٠	Azoospermic partner (vasectomized or due to a medical cause)
	Azoospermia is a highly effective contraceptive method provided that the partner is the sole sexual partner of the woman of childbearing potential and the absence of sperm has been confirmed. If not, an additional highly effective method of contraception should be used.
	participant's medical records, medical examination, or medical history interview.
• co	Highly Effective Methods^b That Are User Dependent Failure rate of $<1\%$ per year when used nsistently and correctly.
•	Combined (estrogen- and progestogen-containing) hormonal contraception associated with inhibition of ovulation ^c
	– oral
	– intravaginal
	– transdermal
	– injectable
٠	Progestogen-only hormone contraception associated with inhibition of ovulation ^c
	– oral
	– injectable
٠	Sexual abstinence
	Sexual abstinence is considered a highly effective method only if defined as refraining from heterosexual intercourse during the entire period of risk associated with the study intervention. The reliability of sexual abstinence needs to be evaluated in relation to the duration of the study and the preferred and usual lifestyle of the participant.

- Effective Methods^d That Are Not Considered Highly Effective Failure rate of ≥ 1% per year when used consistently and correctly.
- Progestogen-only oral hormonal contraception where inhibition of ovulation is not the primary mode of action
- Male or female condom with or without spermicide
- Cervical cap, diaphragm, or sponge with spermicide
- A combination of male condom with either cervical cap, diaphragm, or sponge with spermicide (double-barrier methods)^c
- a) Contraceptive use by men or women should be consistent with local regulations regarding the use of contraceptive methods for those participating in clinical studies.
- b) Failure rate of <1% per year when used consistently and correctly. Typical use failure rates differ from those when used consistently and correctly.
- c) Male condoms must be used in addition to hormonal contraception.
- d) Considered effective, but not highly effective failure rate of ≥1% per year. Periodic abstinence (calendar, symptothermal, post-ovulation methods), withdrawal (coitus interruptus), spermicides only, and lactational amenorrhea method (LAM) are not acceptable methods of contraception.
- e) Male condom and female condom should not be used together (due to risk of failure from friction).

10.5 Appendix: Risk-based Approach

ICH E6-R2 guideline for GCP is introducing the "risk-based approach" concept which permits to focus efforts on what is critical for a study and most specifically on Critical Data and Critical Processes. Critical data and processes are defined for the study with associated risks in the Study Risk Management Plan.

10.6 Appendix: Abbreviations

1/dil	1/dilution
Ab	Antibody
AcNPV	Autographa californica nuclear polyhedrosis virus
AE	Adverse event
AESI	Adverse event of special interest
AR	Adverse reaction
BL	Blood sampling
CI	Confidence interval
CRF	Case report form
CRO	Contract Research Organization
D	Day
DC	Diary card
DNA	Deoxyribonucleic acid
FAS	Full analysis set
FSH	Follicle stimulating hormone
GBS	Guillain-Barré syndrome
GCI	Global Clinical Immunology
GCP	Good Clinical Practice
GDPR	General Data Protection Regulation
GMT	Geometric mean titer
GMTR	Geometric mean titer ratio
GPV	Global Pharmacovigilance
HA	Hemagglutinin
HAI	Hemagglutination inhibition
HRT	Hormonal replacement therapy
IB	Investigator's Brochure
ICF	Informed consent form
ICH	International Council for Harmonization
IEC	Independent Ethics Committee
IIV4	Quadrivalent-inactivated influenza vaccine
IM	Intramuscular
IMP	Investigational Medicinal Product

IRB	Institutional Review Board
IRT	Interactive response technology
KCDC	Korea Centers for Disease Control & Prevention
LLT	Lowest level term
MA	Memory aid
MedDRA	Medical Dictionary for Regulatory Activities
NA	Not applicable
NH	Northern Hemisphere
NIMP	Non- Investigational Medicinal Product
NIP	National Immunization Program
PC	Phone call
PPAS	Per-protocol analysis set
РТ	Preferred term
PY	Person Year
QIV	Quadrivalent influenza vaccine
rHA	Recombinant hemagglutinin
RIV4	Recombinant Influenza Vaccine, Quadrivalent
SAE	Serious adverse events
SafAS	Safety Analysis Set
SAP	Statistical Analysis Plan
SH	Southern Hemisphere
SoA	Schedule of Activities
SOC	System Organ Classes
TBD	To be determined
TIV	Trivalent influenza vaccine
US	United States
USPI	US Prescribing Information
V	Visit
WHO	World Health Organization

11 References

4.2.4.4	Duration of a Participant in the Active Phase	
4.2.4.5	Duration of the Active Phase	19
5	Changes in the Conduct of the Trial or Planned Analyses	20
6	Supporting Documentation	21
6.1	Appendix 1 List of Abbreviations	21
6.2	Appendix 2 Bayesian approach	23
7	References	27

List of Tables

Table 2.1: Objectives and endpoints	6
Table 3.1: Descriptive statistics produced	9

List of Figures

Figure 1.1: Graphical study	y design	5
-----------------------------	----------	---

1 Overall Design

[figure not shown]
This study is a Phase III, parallel, randomized, modified double-blind, active-controlled, multicenter clinical study planned to be conducted in 300 participants 18 years of age and older in South Korea to describe the immunogenicity and safety of the RIV4 versus a locally licensed IIV4 (Fluarix® quadrivalent) that will serve as a control arm.

In each age group (18-49 years of age and \geq 50 years of age), eligible participants will be randomized in a 1:1 ratio through the Interactive Response Technology (IRT) to receive a single intramuscular (IM) injection of either RIV4 or IIV4 at D01.

Participants will attend 2 visits and will provide a pre-vaccination blood sample (BL0001) at D01 and a post-vaccination blood sample (BL0002) at D29. The duration of each participant's participation will be approximately 6 months (180 days).

The design of the study is summarized in Table 4.1 of the protocol.

Figure 1.1: Graphical study design

Abbreviations: BL, Blood sampling; V, Visit; PC, Phone call

Detailed study design is provided in Sections 4.1 and 1.1 of the protocol.

2 **Objectives and Endpoints**

The study objectives and the corresponding endpoints are described in Table 2.1.

Table 2.1: Objectives and endpoints	Table 2.1:	Objectives	and	endpoints
-------------------------------------	-------------------	-------------------	-----	-----------

Primary* Objectives	Primary Endpoints	
Immunogenicity		
• To describe the immune response induced by RIV4 and IIV4 in 18-49 and ≥ 50 years of age participants by HAI measurement method.	 HAI antibody (Ab) titers obtained on Day (D) 01 and D29 Individual HAI titers ratio D29/D01 Seroconversion: titer < 10 (1/dilution [1/dil]) at D01 and post-injection titer ≥ 40 (1/dil) at D29, or titer ≥ 10 (1/dil) at D01 and a ≥ 4-fold increase in titer (1/dil) at D29 Titer ≥ 40 (1/dil) at D01 and D29 Detectable titer ≥ 10 (1/dil) on D01 and D29 	
Safety †		
To describe the safety profile of all participants in RIV4 and IIV4 groups	 Presence of any unsolicited systemic AE reported in the 30 minutes after vaccination Presence of solicited injection site, and systemic reactions occurring up to 7 days after vaccination, (ie, pre-listed in the participant's diary card [DC] and case report form [CRF]) Presence of unsolicited (spontaneously reported) AEs up to 28 days after vaccination Presence of serious adverse events (SAEs), including adverse events of special interest (AESIs), throughout the trial period Other endpoints recorded or derived as described in Section 4.2 	

*This study has no secondary or exploratory objectives.

† Details on safety endpoints (terminology, definitions, and intensity scales) are presented in Table 10.1 and Table 10.2 of the protocol.

3 Statistical Considerations

3.1 Statistical Hypotheses

No hypotheses will be tested. All analyses will be descriptive.

3.2 Sample Size Determination

A total of approximately 300 participants will be enrolled as follows:

- 75 participants from 18 to 49 years of age in RIV4 group
- 75 participants \geq 50 years of age in RIV4 group
- 75 participants 18 to 49 years of age in IIV4 group
- 75 participants \geq 50 years of age in IIV4 group

Assuming a drop-out rate of 5%, a total of 71 evaluable participants per group of age and vaccine is anticipated.

No formal power calculation has been performed, but based on the planned sample size the estimation precision is provided as follows:

For proportions, the expected precision of estimation (using PASS14) is: 71 participants per treatment group provide a maximum width of 95% confidence interval (CI) of 24.2% for single proportions and a maximum width of 95% CI of 32.0% for differences between proportions (when the group proportions are 50%).

For quantitative data, the distance from the mean to the limits of 95% CI is equal to 0.154 for single mean and 0.216 for difference in means (when the estimated standard deviation is 0.65).

In case of any unexpected situations where this planned number is not reached (due to an unexpected high number of withdrawals or unevaluable data) then additional participants might be recruited before database lock to achieve that planned sample size. Such assessment and decision will be performed in a blind manner during the course of the trial before database lock or any statistical analysis.

3.3 Populations for Analysis

The following populations for analysis are defined:

Safety Analysis Set (SafAS)

Safety Analysis Set (SafAS): Participants who have received a dose of the study vaccines. All participants will have their safety analyzed according to the vaccine they actually received. Safety data recorded for a vaccine received out of the protocol design will be excluded from the analysis (and listed separately). SafAS will be used for safety analyses.

Full analysis set (FAS)

Full analysis set (FAS): Subset of randomized participants who received a dose of the study vaccine and had a post-vaccination blood sample. Participants will be analyzed according to the intervention to which they were randomized. The FAS will be used for immunogenicity analysis.

Per-protocol analysis set (PPAS)

Per-protocol analysis set (PPAS): Subset of the FAS. Participants presenting with at least one of the following conditions will be excluded from the PPAS:

- Participant did not meet all protocol-specified inclusion criteria or met at least one of the protocol-specified exclusion criteria
- Participant did not receive vaccine
- Participant received a vaccine other than the one that he/she was randomized to receive
- Preparation and/or administration of vaccine was not done as per-protocol
- Participant did not receive vaccine in the proper time window
- Participant did not provide the post-dose serology sample at Visit 2 in the proper time window, or a post-dose serology sample was not drawn
- Participant received a protocol-prohibited therapy/medication/vaccine

PPAS will be used for immunogenicity analysis.

Participants with data in CRF

Participants with data in CRF: Participants with data in CRF are participants for whom data were recorded at a visit.

Randomized participants

Randomized participants: a randomized participant is a participant for whom a randomized group has been allocated by IRT.

Participants with data in CRF and randomized participants will be used to summarize participants' disposition, demographic and baseline characteristics.

3.4 Statistical Analysis

3.4.1 General Considerations

The statistical analysis will be performed under the responsibility of the Sponsor's Biostatistics platform using SAS® Version 9.4 or later.

No hypotheses testing was planned in this study. All statistical analysis results will be provided by age group and by vaccine group. No replacement will be done for safety and immunogenicity missing data and outliers. Analysis will be done using the collected data. Nevertheless, for unsolicited systemic AEs, missing relationship will be considered as related to study vaccine at the time of analysis.

For descriptive purposes, the following statistics will be presented:

Disposition and	Categorical data	Number of participants
follow-up description	Categorical data	Percentage of participants
	Continuous data	Mean, standard deviation (SD), minimum and maximum.
Baseline	Categorical data	Number of participants.
characteristics		Percentage of participants.
	Continuous data	Mean, standard deviation (SD), quartiles, minimum and maximum.
Clinical safety results	Categorical data	Solicited: Number and percentage (95% CIs) of participants.
		Unsolicited: Number and percentage (95% CIs) of participants and number of events.
Immunogenicity results	Categorical data (seroconversion, cutoff)	Number and percentage (95% CIs) of participants.
	Continuous data	Log10: Mean and standard deviation.
	(titer / data)	Anti-Log10 (work on Log10 distribution, and anti- Log10 applied): Geometric mean, 95% CI of the geometric mean, quartiles, minimum, and maximum.
		Graphical representation by Reverse Cumulative Distribution Curve (RCDC).

 Table 3.1: Descriptive statistics produced

The CI for the single proportion will be calculated using the exact binomial method (Clopper-Pearson method, quoted by Newcombe (1), i.e., using the inverse of the beta integral with SAS®).

For immunogenicity results, assuming that Log10 transformation of the titers / data follows a normal distribution, at first, the mean and the 95% CI will be calculated on Log10 (titers / data) using the usual calculation for normal distribution (using Student's t distribution with n-1 degree of freedom), then antilog transformations will be applied to the results of calculations, in order to provide geometric means (GMs) and their 95% CI.

3.4.2 Primary Endpoints

The primary endpoints for immunogenicity and safety are shown in Table 2.1.

3.4.2.1 Immunogenicity

The analysis of Hemagglutinin inhibition (HAI) Ab response measured at D01 and D29 will be performed by age subgroup, intervention group and pooled age group, including but will not be limited to:

- Geometric mean of HAI Ab titer (GMT) and 95% CI at D01 and D29
- Geometric mean fold-rise (GMFR) of HAI Ab titer and its 95%CI. Fold-rise is computed as individual titer ratio of post-vaccination value divided by baseline value.
- Number and percentage of participants with seroconversion (seroconversion rate): titer < 10 (1/dilution [1/dil]) at D01 and post-injection titer ≥ 40 (1/dil) at D29, or titer ≥ 10 (1/dil) at D01 and a ≥ 4-fold increase in titer (1/dil) at D29
- Number and percentage of participants with titer ≥ 40 (1/dil) at D01 and D29
- Number and percentage of participants with detectable titer ≥ 10 (1/dil) at D01 and D29

The 95% CIs for the GMTs and GMFR will be calculated using a normal approximation of log_{10} -transformed titers. The 95% CIs for the proportions will be based on the Clopper-Pearson method (1).

The ratios of GMTs (RIV4/IIV4) in each age group and pooled age group will be obtained between groups with the 95% CIs calculated using a normal approximation of log₁₀-transformed titers. The differences in the seroconversion rates between groups in each age group and pooled age group will be computed along with the 2-sided 95% CIs by the Wilson-Score method without continuity correction (2).

Reverse cumulative distribution curves in each age group and pooled age group against each strain will be performed for baseline (D01) and post-vaccination immunogenicity (D29).

The primary immunogenicity analyses will be performed on the Per-Protocol Analysis Set (PPAS) and on the Full Analysis Set (FAS). Details of both analyses sets are described in Section 3.3.

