8.1.2 Immunogenicity Assessments

The HAI assay is the main test that detects Ab directed against the HA antigen and is commonly used to assess the immunogenicity of influenza vaccines. HAI Ab titers to each virus strain represented in the vaccine will be measured in sera obtained at baseline (D01) and 28 days after immunization (D29).

All methods will be performed at a Sanofi Pasteur laboratory or at a qualified contract laboratory under Sanofi Pasteur's responsibility, as described below. Test serum samples and quality control sera (sheep, ferret, and / or human sera) are incubated with Sigma Type III neuraminidase (NA) from *Vibrio cholerae* to eliminate non-specific inhibitors. Adsorption of spontaneous anti-species agglutinins are then performed by incubating the test serum samples and quality control sera with a red blood cell (RBC) suspension. Following this, the mixtures are centrifuged and the supernatants containing the treated sera are collected for testing. Ten 2-fold dilutions (starting at 1:10) of the treated test serum samples and quality control sera are incubated with a previously titrated influenza antigen at a concentration of 4 hemagglutination units (HAU) / 25 μ L. Influenza antigen is not added to the serum control wells containing only serum and RBCs. The mixture is then incubated and a RBC suspension is added. Following incubation, the results are read. The

endpoint of the assay is the highest serum dilution in which complete inhibition of hemagglutination occurred. Each serum sample can either be tested in singleton (ie, one assay run) or in 2 independent assay runs (duplicate) which will include 2 independent samplings of the original serum and 2 independent preparations of influenza virus antigen. The lower limit of quantitation (LLOQ) is set at the lowest dilution used in the assay, 1:10. Titers below this level are reported as < 10 (1/dilution [dil]). If the highest / last serum dilution used in the assay exhibited complete inhibition of hemagglutination, the serum Ab titer is reported as $\ge 10 240$ (1/dil).

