9.4.2 Immunogenicity

Descriptive analyses on HAI Ab response measured at D01 and D29 will be performed in each age, intervention group and pooled age group, including but will not be limited to:

- Geometric mean of HAI Ab titer (GMT) and 95% CI at D01 and D29
- Geometric mean fold-rise (GMFR) of HAI Ab titer and 95%CI. Fold-rise is computed as individual titer ratio of post-vaccination value divided by baseline value.
- Number and percentage of participants with seroconversion (seroconversion rate): titer < 10 (1/dilution [1/dil]) at D01 and post-injection titer ≥ 40 (1/dil) at D29, or titer ≥ 10 (1/dil) at D01 and a ≥ 4-fold increase in titer (1/dil) at D29
- Number and percentage of participants with titer $\ge 40 (1/dil)$ at D01 and D29
- Number and percentage of participants with detectable titer ≥ 10 (1/dil) at D01 and D29

The 95% CIs for the GMTs and GMT ratios (GMTRs) will be calculated using a normal approximation of log-transformed titers. The 95% CIs for the proportions will be based on the Clopper-Pearson method. The ratios of GMTs (RIV4/IIV4) in each age group will be obtained between groups with the 95% CIs calculated using a normal approximation of log-transformed titers. The differences in the seroconversion rates between groups in each age group will be computed along with the 2-sided 95% CIs by the Wilson-Score method without continuity correction. Additional parameters may be displayed as appropriate.

In addition, as a complementary analysis to support bridging discussion, Bayesian method will be used to evaluate the probability of non-inferiority in GMTs. The posterior probability of the true ratio of GMTs (RIV4/IIV4) to be higher than the commonly accepted non-inferiority margin (0.667) will be calculated using the Bayesian approach to support bridging with previous non-inferiority trials. Further details about the statistical methodology will be provided in the SAP.

Reverse cumulative distribution curves in each age group against each strain will be performed for baseline (D01) and post-vaccination immunogenicity (D29).

The Full Analysis Set (FAS) and Per-Protocol Analysis Set (PPAS) will be used for the main immunogenicity analyses. Details of both analyses' sets are described in Section 9.3.

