4.2.3 Immunogenicity

4.2.3.1 Computed Values for Analysis

In order to appropriately manage extreme values (< LLOQ and \geq ULOQ) for analysis purposes, the following computational rule is applied to the values provided in the clinical database for each blood sample (BL) drawn:

- If a value is < LLOQ, then use the computed value LLOQ/2
- If a value is between \geq LLOQ and < ULOQ, then use the value
- If a value is \geq ULOQ, then use the computed value ULOQ

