6.2 Appendix 2 Bayesian approach

Calculation of the posterior probability of the GMT ratio being > 0.667

Based on Bayesian approach (3), we are going to calculate the posterior probability of the true GMT ratio for each strain between RIV4 and IIV4 to be higher than the commonly accepted non-inferiority margin (0.667), which is equivalent to true mean difference on the log_{10} scale > -0.176.

We assume that HAI log₁₀titer x_i for each strain for any group IIV4 or RIV4 follows normal distributions with known variance σ^2 . Considering the following sampling model for data from the two groups:

$$\begin{aligned} X_{i,1} = \mu + \delta + \epsilon_{i,1} \\ X_{i,2} = \mu - \delta + \epsilon_{i,2} \\ \{\epsilon_{i,j}\} \sim i. i. d. normal (0, \sigma^2) \end{aligned}$$

Using this parameterization where $\theta_1 = \mu + \delta$ and $\theta_2 = \mu - \delta$, representing group mean on the \log_{10} scale for each group. We see that δ represents half the population difference in means, as $(\theta_1 - \theta_2)/2 = \delta$, and μ represents the pooled average, as $(\theta_1 + \theta_2)/2 = \mu$. Assuming standard deviation of HAI \log_{10} titer is known and equal to the sample standard deviation for each strain. Sine σ is known, no prior is needed for it. Convenient conjugate prior distributions for the unknown parameters μ , δ are

$$p(\mu, \delta) = p(\mu) \times p(\delta)$$
$$\mu \sim normal(\mu_0, \gamma_0^2)$$
$$\delta \sim normal(\delta_0, \tau_0^2)$$

Then the full conditional distribution of μ and δ are as follows:

$$\{\mu | x_{i,1}, x_{i,2}, \delta, \sigma^2\} \sim normal(\mu_n, \gamma_n^2), \text{ where}$$
$$\mu_n = \gamma_n^2 \times [\mu_0 / \gamma_0^2 + \sum_{i=1}^{n_1} (x_{i,1} - \delta) / \sigma^2 + \sum_{i=1}^{n_2} (x_{i,2} + \delta) / \sigma^2]$$
$$\gamma_n^2 = [1 / \gamma_0^2 + (n_1 + n_2) / \sigma^2]^{-1}$$

$$\{\delta | x_{i,1}, x_{i,2}, \mu, \sigma^2\} \sim normal(\delta_n, \tau_n^2), \text{ where}$$

$$\delta_n = \tau_n^2 \times [\delta_0 / \tau_0^2 + \sum_{i=1}^{n_1} (x_{i,1} - \mu) / \sigma^2 - \sum_{i=1}^{n_2} (x_{i,2} - \mu) / \sigma^2]$$

$$\tau_n^2 = [1/\tau_0^2 + (n_1 + n_2) / \sigma^2]^{-1}$$

For the prior distribution of μ and δ , with reference to US studies (PSC12 and PSC16) we give prior settings as Appendix Table 1 shown. The priors on γ_0^2 and τ_0^2 tend to make these prior

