Appendix Table 1: prior settings for unknown parameters

Therefore, based on the above prior distribution, we can then calculate the posterior probability Pr ($2\delta > -0.176$ |data). The Markov chain Monte Carlo (MCMC) procedure is utilized to obtain samples from the posterior distribution. SAS example code is provided below.

The statistical criterion for demonstrating success (posterior probability threshold) is not proposed due to the not powered sample size and the nature of the descriptive study. But the corresponding threshold might be proposed in the bridge report for descriptive evaluation purpose.

Appendix Figure 1: Prior and posterior distributions for δ given a hypothetical observed data with $\delta = 0, \mu = 2.5, \sigma = 0.65$

```
SAS example code for the posterior probability calculation:
data aa;
 set add.adis;
 if paramn=1 and avisitn=2; ***paramn: parameter index in ADaM adis. Sample code only focus
on one parameter;
                 ***avisitn=2 is used to filter the post-vaccination titers.
 avallog=log10(aval);
 keep usubjid param paramn trt01pn trt01p aval avallog;
run;
/*==
     /*get the poopled mean and SD from data */
proc summary data=aa;
 var avallog;
 output out= stats(drop= type freq ) mean=mu pool n=n std=SD;
run;
/*got the group mean difference between RIV4 and IIV4*/
ods listing close;
ods output statistics = stats diff;
proc ttest data=aa alpha=0.05 ci=equal;
 class trt01pn ;
 var avallog;
run;
ods listing;
/*set initial value to mu pool, del; set SD as a fixed value obtained from data*/
proc sql noprint;
 select mean/2 into: del from stats diff (where=(method="Pooled"));
 select mu pool into: mu pool from stats ;
 select sd into: sd from stats ;
quit;
%put &del. &mu pool. &sd.;
/*======Start MCMC procedures:=====*/
/*generate posterior samples for mu and del*/
proc mcmc data=aa outpost=postout seed=123 nmc=10000 thin=2 monitor=( parms ) statistics;
                                      *** Postsumint= summary statistics;
 ods select PostSumInt;
 parm mu pool &mu pool. del &del.;
/* specify parameters to estimate and assign initial values to them*/
 prior mu_pool ~ normal(mean=2, var=1); /*specify prior distributions for the parameter mu that
represents the pooled average */
 prior del ~ normal(mean=-0.088, var=100);
```

Confidential/Proprietary Information Page 25 of 27 /*enable different avallog to have different mean and variance, depending on their group indicator*/

```
if trt01pn = 1 then do;

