mu = mu_pool + del;
end;
else do;
mu = mu_pool - del;
end;
s2=&sd. * &sd.; /*Assuming standard deviation of HAI log10 titer is known and equal to the
sample standard deviation*/
model avallog ~ normal(mu, var=s2);
run;
```

```
/*get the posterior probability of the GMT ratio being > 0.667, which is equivalent to mean
difference on the log10 scale > -0.176.*/
proc format;
value delfmt low- -0.088=" mean difference on the log10 scale <= -0.176"
        -0.088 <- high= ' mean difference on the log10 scale > -0.176';
```

run;

```
ods output OneWayFreqs=stat1;
proc freq data = postout;
tables del /nocum;
format del delfmt.;
run;
```

7 References

- 1. Newcombe RG. Two-sided confidence intervals for the single proportion: comparison of seven methods. Stat Med. 1998;17(8):857-72.
- 2. Newcombe RG. Interval estimation for the difference between independent proportions: comparison of eleven methods. Stat Med. 1998;17(8):873-90.
- 3. Hoff PD. A First Course in Bayesian Statistical Methods. Springer-Verlag, New York, Springer Texts in Statistics, 2009.

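### The RIV4/IIV4 Day 29 GMT ratio and its posterior probability are not adjusted for the same-strain Day 1 titer, so precision available from data already collected is given up

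*SAP*

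**What the plan says.** Protocol 9.4.2 reads: "The ratios of GMTs (RIV4/IIV4) in each age group will be obtained between groups with the 95% CIs calculated using a normal approximation". SAP 3.4.2.1 repeats this and adds the pooled age group: "The ratios of GMTs (RIV4/IIV4) in each age group and pooled age group will be obtained between groups with the 95% CIs calculated". Neither names a covariate.

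SAP Appendix 2 models the two group means as mu + delta and mu − delta, with a standard deviation that "is known and equal to the sample standard deviation for each strain". Its example code selects post-vaccination titers, then retains only these variables: "keep usubjid param paramn trt01pn trt01p aval avallog". No baseline value is among them. The likelihood is "model avallog ~ normal(mu, var=s2", where the mean depends on vaccine group alone.

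Baseline titers will exist. Protocol 8.1.2 says HAI titers to each vaccine strain "will be measured in sera obtained at baseline (D01) and 28 days after immunization (D29". SAP 3.4.2.1 uses them for D01 summaries and reverse cumulative curves, for the geometric mean fold-rise and for seroconversion. It specifies no baseline-adjusted ratio between vaccines. The wording that the analyses are not limited to those listed leaves room for one but does not prespecify it.

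**The concern.** A participant's titer before vaccination may predict the titer after it. Where it does, comparing D29 means without the D01 value leaves explainable variation in the standard error. Randomization is 1:1 within age group only, so D01 titers are balanced between arms by chance alone, with about 71 per arm in each age group.

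The plan sizes the study on precision, and SAP 3.4.2.3 says the posterior probability is calculated to support bridging with earlier non-inferiority trials. A D01 imbalance would show in the baseline tables, but the plan has no prespecified way to say how much of the observed ratio it accounts for. An adjusted ratio produced after seeing such an imbalance would be post hoc.

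**Working it through.** **Inputs.** SD 0.65 and 71 evaluable per age-by-vaccine group come from SAP 3.2. The margin 0.667 (−0.176 on the log10 scale) comes from Appendix 2. The D01–D29 correlation, rho, is in neither document; 0.3 to 0.7 is assumed, with lower values also shown.

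**The plan's own figure.** SE = 0.65 × √(2/71) = 0.1091. Half-width = t(140) × 0.1091 = 0.2157, which matches the stated 0.216. As a factor around the ratio, 10^0.2157 = 1.64.

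**With a D01 covariate.** Half-width = t(139) × 0.1091 × √(1 − rho²). The lower limit at an observed ratio of 1 is 10^(−half-width). The posterior probability at an observed ratio of 1 is Φ(0.176 / [0.1091 × √(1 − rho²)]); the Appendix 2 priors are too diffuse to matter. The posterior column takes sigma as the residual SD.

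| One age group, 71 per arm | Half-width | Factor | Lower limit | P(ratio > 0.667) |
|---|---|---|---|---|
| Unadjusted | 0.216 | 1.64 | 0.61 | 0.947 |
| rho 0.3 | 0.206 | 1.61 | 0.62 | 0.955 |
| rho 0.5 | 0.187 | 1.54 | 0.65 | 0.969 |
| rho 0.7 | 0.154 | 1.43 | 0.70 | 0.988 |

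At rho 0.1 and 0.2 the half-width is 0.215 and 0.211. Allowing for small-sample covariate imbalance adds about 0.001 to the adjusted half-widths. The lower limit passes 0.667 only when √(1 − rho²) falls below 0.176/0.2157 = 0.816, that is, rho above about 0.58.

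**Pooled ages (142 per arm, same SD assumed).** Unadjusted half-width = t(282) × 0.65 × √(2/142) = 0.152, lower limit 0.705. At rho 0.3, 0.5 and 0.7 the half-width is 0.145, 0.132 and 0.108, and the limit 0.716, 0.739 and 0.779. The posterior at an observed ratio of 1 goes from 0.989 to 0.992, 0.996 and 0.999.

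**Chance imbalance.** A D01 difference of one standard error shifts the unadjusted log10 ratio by rho × 0.1091. The ratio then moves by a factor of 10^(0.3 × 0.1091) = 1.08, or 1.13 or 1.19 at rho 0.5 or 0.7, in one age group.

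**Effect of the fixed sigma.** If the covariate is added but sigma stays at the raw sample SD, the posterior SD of the log10 ratio stays at 0.109. In 40,000 simulated trials with equal vaccines and 71 per arm, the median posterior stayed at 0.95 at all three correlations. With the residual SD it rose to 0.954, 0.969 and 0.988.

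**Undetectable baseline titers.** SAP 4.2.3.1 says: "If a value is < LLOQ, then use the computed value LLOQ/2", so D01 values below 10 all become 5. Assuming normal log10 D01 titers with SD 0.65 and an underlying GMT of 20 or 10, about 32% or 50% would fall below 10. A correlation of 0.5 would then act like 0.47 or 0.44, with a half-width of about 0.19.

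**The case against.** The strongest reply is that nothing in the plan is wrong. The study tests no hypothesis, claims no power and sets no posterior threshold, and the stated precision figures reproduce. Whether a lower limit passes 0.667 changes no planned conclusion. All of this stands, so the point is about efficiency and prespecification.

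The gain also rests on a correlation the documents do not give. At 0.3 it is about 4% of the interval width, and the pooled posterior at an observed ratio of 1 rises by only about 0.01 even at 0.7. That stands too, and is why a range is shown.

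Third, lost precision and retained imbalance are two views of the same variance. The planned interval already allows for the imbalance, and a shift of 1.08 to 1.19 lies well inside ×/÷1.64. This is right: the imbalance is not an added bias. Adjustment would still show how much of an observed shift goes with D01.

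Fourth, D01 already enters through fold-rise and through the planned between-vaccine difference in seroconversion rates. Neither gives an adjusted GMT ratio. Fold-rise is listed within arm only. With equal D01 and D29 SDs its SD is 0.65 × √(2(1 − rho)) = 0.77 at rho 0.3, so a fold-rise contrast would be less precise than the plain D29 contrast whenever rho is below 0.5.

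**Conclusion.** The concern holds as an improvement the plan should make. Neither the GMT ratio nor the Appendix 2 probability uses the D01 titer, although it is collected for every strain. Per age group, adjustment would narrow the interval by about 5%, 13% or 29% at a correlation of 0.3, 0.5 or 0.7 (1 − √(1 − rho²)), and by almost nothing at 0.1. The sizes assume SD 0.65, 71 evaluable per arm, a common linear D01 slope and an undocumented correlation. Strains with many undetectable D01 titers would gain less. The planned unadjusted ratio remains valid.

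**What to change.** In SAP 3.4.2.1, prespecify an ANCOVA of log10 D29 titer on vaccine group and same-strain log10 D01 titer within each age group, adding age group as a term in the pooled analysis. Report the adjusted ratio and 95% CI beside the unadjusted ratio, which is kept for reading against the earlier studies. State in advance the role of each in the bridging discussion.

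In Appendix 2, add a second run with the D01 term, a stated diffuse normal prior on its slope, and sigma fixed at the residual SD from that ANCOVA.

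State that the adjusted analysis uses participants with both D01 and D29 results, and give their number. The FAS is defined as "Subset of randomized participants who received a dose of the study vaccine and had a post-vaccination blood sample", so a member without a D01 result would drop out of the adjusted ratio.

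The cost is one paragraph, a slope, prior and sigma change in the Appendix 2 model and code, and one degree of freedom. The output grows by one line per strain in each table: 4 strains × 3 age presentations × 2 analysis sets = 24 adjusted ratios, plus the second set of posterior probabilities. No new data are needed.
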